2. STUDY OBJECTIVES

2.1 Primary Objective

The primary objective of this study is to evaluate the risk of developing EFAD in pediatric patients, including neonates, receiving either Clinolipid or SOC 100% SO-based ILE (Intralipid) as a component of PN within the hospital setting from 7 up to 90 days.

Complete FA profile will be regularly assessed and EFAD will be defined using a Holman Index (plasma triene:tetraene ratio, specifically 5,8,11-eicosatrienoic acid [mead acid] to 5,8,11,14 eicosatetraenoic acid [arachidonic acid, ARA] ratio) value of >0.4 in the context of low LA, low ARA, and high eicosatrienoic acid.

Genetic polymorphisms in the fatty acid desaturase 1 gene (FADS1) and fatty acid desaturase 2 gene (FADS2) will also be assessed in a subset of patients (approximately 20%) and the distribution of the polymorphisms will be assessed in the context of the FA profile as the synthesis of gamma-LA and ARA from LA (n-6 pathway) and the synthesis of stearidonic acid, eicosapentaenoic acid (EPA) and docosahexaenoic acid (DHA) from ALA (n-3 pathway) require both the delta-5 and delta-6 desaturase enzymes (coded for by FADS1 and FADS2 genes). Genetic material will be obtained from buccal smears in all patients with consent to analysis of FADS1 and FADS2 polymorphisms. From the subset of patients consenting to genetic analysis, the 10 patients (5 Intralipid and 5 Clinolipid) with the lowest levels of ARA at any point during the study and the10 patients (5 Intralipid and 5 Clinolipid) with the highest levels of ARA at any point during the study will be selected for analysis of single nucleotide polymorphisms (SNPs) within FADS 1 and FADS2 genes.

2.2 Secondary Objective(s)

The secondary objectives in patients receiving either Clinolipid or Intralipid are to evaluate:

- The risk of developing liver disease including PNALD:
 - PNALD will be defined by direct bilirubin ≥2 mg/dL when no other etiology for liver dysfunction is present;
 - Hepatic integrity will be assessed by measuring plasma liver function tests: alkaline phosphatase (ALP), aspartate aminotransferase (AST), alanine aminotransferase (ALT), gamma-glutamyl transferase (GGT), and total and direct bilirubin;
 - Plasma main phytosterols (stigmasterol, campesterol, sitosterol), cholesterol and squalene levels will be assessed. Phytosterols levels will be correlated with the risk of developing PNALD.
- The adequacy of nutritional interventions:
 - Prescribed and actual nutritional intakes (energy, protein, carbohydrates, and lipid) from both PN and enteral/oral nutrition will be collected and recorded on a daily basis and summarized on a daily basis during the first 2 weeks of treatment and on an approximately 15-day basis afterwards up to the end of study treatment in each of the treatment groups.
 - Growth will be assessed and evaluated from baseline to end of study treatment on an approximately every 15-day basis using descriptive summary statistics for weight, and height/length (and head circumference in infant <1 year) in each of the treatment groups as follows:
 - Gain in weight (g/kg/day in infants <1 year of age, g/day in children and adolescents) and gain in length/height (mm/week in all) and head circumference (mm/week in infants <1 year);
 - Changes in the standard deviation score (SDS or z-score) from reference growth curves (Fenton growth curve for premature infants, World Health Organization (WHO) growth standards for infants and children ages 0 to 2 years, or Center for Disease Control (CDC) growth charts for children age ≥2 years).

- The safety profiles of Clinolipid and Intralipid, as assessed by adverse events (AEs), serious adverse events (SAEs) and AEs of special interest (AESIs)
 - AESIs are known AEs related to PN with ILEs, per Intralipid and Clinolipid United States Prescribing Information (USPI) and include the following: catheter related infection, thrombophlebitis; EFAD as well as ILE-related Immediate or Early adverse reactions including: dyspnea, cyanosis, allergic reactions, hyperlipemia, hypercoagulability, nausea, vomiting, headache, flushing, increase in temperature, sweating, sleepiness, pain in the chest and back, slight pressure over the eyes, dizziness, irritation at the site of infusion, and ILE-related delayed adverse reactions including: hepatomegaly, jaundice, splenomegaly, thrombocytopenia, leukopenia, transient increases in liver function tests, and overloading syndrome (focal seizures, fever, leukocytosis, hepatomegaly, splenomegaly and shock).

3. INVESTIGATIONAL PLAN

3.1 Overall Study Design and Plan

This is a multi-center, randomized, double-blind, controlled, safety and efficacy study to evaluate the occurrence of EFAD (diagnosed by Holman Index >0.4) in pediatric patients receiving either Clinolipid or SOC SO-based ILE (Intralipid) in the hospital setting from 7 up to 90 days as part of PN. The risk of developing liver disease, including PNALD (defined by direct bilirubin $\geq 2 \text{ mg/dL}$) when no other etiology for liver dysfunction is present, also will be assessed.

Approximately 100 pediatric patients, including neonates, will participate in the study. Patients will be randomized in a 1:1 ratio to the treatment groups (Clinolipid or Intralipid) according to a central dynamic randomization scheme stratified by site and age group (premature infants born <37 weeks of gestation up to 1 month corrected age (CA), full-term neonates born \geq 37 weeks of gestation to <1 month of age, infants 1 to <12 months of age, children 1 to <10 years of age, adolescent 10 to <18 years of age). In the case of multiple birth pregnancies, the infants will be assigned to the same treatment group.

Holman Index and FA profile will be evaluated. Select polymorphisms in the FA desaturase genes FADS1 and FADS2, will be determined in a subset of patients. The major plasma phytosterols found in the ILEs (stigmasterol, campesterol, sitosterol), cholesterol, and squalene will also be assessed.

The study consists of a Screening Period to confirm the patient's eligibility for the study after the informed consent form (ICF) is signed and a Study Treatment Period starting when the patient receives study treatment (See Appendix 1, Schedule of Events Table). End of study treatment is defined as the last day of PN with Intralipid or Clinolipid; maximum 90 days of study treatment is allowed.

3.2 Rationale for Study Design and Control Group

This will be a descriptive study designed to evaluate the propensity for hospitalized pediatric patients treated adequately with Clinolipid or SOC (Intralipid) from 7 up to 90 days to develop EFAD. Additionally, this study design will evaluate the safety and efficacy of using Clinolipid or Intralipid in a pediatric population.

A double-blind study is appropriate to decrease clinician and patient bias during study conduct.

3.3 Study Duration

Enrollment for the study is anticipated to continue for approximately 22 months after initiation of the study.

4. STUDY POPULATION SELECTION

4.1 Study Population

Approximately 100 pediatric patients, including neonates, will be enrolled in the study.

The study will be conducted in approximately 15 study centers in the United States, focusing on institutions with neonatal and pediatric intensive care units.

A patient will be considered to be enrolled in the study after the signing of the ICF and confirmation of compliance with the study inclusion/exclusion criteria. Since this study is being conducted in a pediatric population, the patient's legal representative must provide IC (i.e. sign and date the ICF). An assent form (child's agreement to participate) will also be used following requirements of local or central Institutional Review Board (IRB) as applicable. The patient's legal representative must provide IC (i.e. sign and date the ICF). Screening failures will be documented. Screen failures may be re-screened once, if approved by the medical monitor. All re-screens must be fully re-consented and repeat all screening procedures.

4.2 Inclusion Criteria

Each patient must meet ALL of the following criteria to be enrolled in the study.

- 1. Patients and/or their legal representative must be able to understand the study and voluntarily sign the informed consent form (ICF) per 21 CFR Part 50.55(e)
- 2. Patients and/or their legal representative accept adherence to protocol requirements
- 3. Patients who are expected to require PN for at least 7 days
- Premature infants (born at 24 to <37 weeks of gestation with a birth weight ≥750g) require at least 80% of targeted energy requirements by PN at study entry (up to 1 month CA); full term infants and children require at least 70% of targeted energy requirements by PN at study entry

4.3 Exclusion Criteria

Patients who meet ANY of the following criteria will be excluded from the study:

- Patients who are not expected to survive hospitalization or with a severe critical unresponsive illness at time of initiation with foreseeable intercurrent events that could jeopardize the patient's participation in the study, as judged by the Investigator (e.g., unresponsive shock, sepsis, renal failure requiring dialysis, severe unresponsive metabolic acidosis, and/or severe unresponsive metabolic disorders);
- 2. Patients with a known hypersensitivity to lipid emulsion, egg or soybean proteins, or any of the active substances, excipients, or components of the container or who have a history of an adverse event due to ILE;
- 3. Patients with liver disease including cholestasis;
- 4. Patients with severe hyperlipidemia or severe disorders of lipid metabolism characterized by hypertriglyceridemia (triglyceride >400 mg/dL);
- 5. Patients who are unable to tolerate the necessary laboratory monitoring;
- 6. Patients who are enrolled in another clinical trial involving an investigational agent;
- 7. Patients with a known history of either severe hemorrhagic or severe hemolytic disease as judged by the investigator;
- 8. Premature infants born <24 weeks of gestation and patients ≥ 18 years;
- 9. Premature infants with a birth weight <750 g;
- 10. Patient requires or is expected to require propofol for sedation;
- 11. Patient, born to a symptomatic mother diagnosed with COVID-19 at time of birth or before birth;
- 12. Patient has received a diagnosis of COVID-19 (diagnosis <2 months prior and/or symptoms have not resolved);
- 13. Female patients who are pregnant. Note: All female patients ≥12 years of age must have a negative urine human chorionic gonadotropin (hCG) pregnancy test at screening. For female patients <12 years of age, a urine hCG test at screening will be performed at the discretion of the investigator based on childbearing potential.

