- Hepatic function tests including alkaline phosphatase (ALP), aspartate aminotransferase (AST), alanine aminotransferase (ALT), gamma-glutamyl transferase (GGT), total and direct bilirubin to assess hepatic function and integrity;
- Plasma phytosterol (stigmasterol, campesterol, and sitosterol), cholesterol and squalene levels to determine potential correlation with the development of PNALD;
- Holman Index and fatty acid profiles will be evaluated. Select polymorphisms in the fatty acid desaturase genes, FADS1 and FADS2, will be determined in a subset of patients. The major plasma phytosterols found in the lipid emulsions (stigmasterol, campesterol, and sitosterol), cholesterol, and squalene also will be assessed.

After end of study treatment (maximum of 90 days), the patient will resume PN therapy as prescribed by their healthcare provider.

Study Population:

Key Inclusion Criteria:

- 1. Patients who are expected to require PN for at least 7 days;
- Premature infants (born at 24 to <37 weeks of gestation with a birth weight ≥750 g) must require at least 80% of targeted energy requirements by PN at study entry (up to 1 month CA); full term infants and children must require at least 70% of targeted energy requirements by PN at entry into the study;
- 3. A patient, or legal representative, has signed a written informed consent form per 21 CFR Part 50.55(e).

Key Exclusion Criteria:

- 1. Patients who are not expected to survive hospitalization or with a severe critical unresponsive illness at time of initiation with foreseeable intercurrent events that could jeopardize the patient's participation in the study (i.e. unresponsive shock, sepsis, renal failure requiring dialysis, severe unresponsive metabolic acidosis, and/or severe unresponsive metabolic disorders), as judged by the Investigator;
- 2. Patients with a known hypersensitivity to lipid emulsion, egg or soybean proteins, or any of the active substances, excipients, or components of the container or who have a history of an adverse event due to ILE;

- 3. Patients with liver disease including cholestasis;
- 4. Patients with severe hyperlipidemia or severe disorders of lipid metabolism characterized by hypertriglyceridemia (i.e. triglyceride >400 mg/dL);
- 5. Premature infants born <24 weeks of gestation and patients ≥ 18 years;
- 6. Patient requires or is expected to require propofol for sedation;

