5.1.1.1 Clinolipid Contraindications per US Prescribing Information

The use of Clinolipid is contraindicated in patients with the following:

- Known hypersensitivity to egg or soybean proteins or to any of the ingredients, including excipients.
- Severe hyperlipidemia (serum triglyceride concentrations above 1000 mg/dL) or severe disorders of lipid metabolism characterized by hypertriglyceridemia.

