5.1.2.1 Intralipid Contraindications per US Prescribing Information

The administration of Intralipid 20% is contraindicated in patients with disturbances of normal fat metabolism such as pathologic hyperlipemia, lipoid nephrosis or acute pancreatitis if accompanied by hyperlipidemia.

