5.5 Blinding

The study will be double-blinded. The study treatment assignment will not be known by the Sponsor's or designee's data management, biostatistician (with the exception of an unblinded Sponsor's statistician who will have access to the randomization assignments), and medical functions; Investigator and site personnel; or by the personnel at the central laboratory. In order to prepare the study treatment, the designated pharmacist(s) will be aware of the study treatment (unblinded).

The unblinded pharmacist(s) will prepare the treatment according to the randomization schedule and will enter the required information on the study drug labels. These labels will not contain specific information pertaining to the identity of the study treatment. In addition, specified fields on the label will be blank so that the pharmacist(s) can enter the patient number, as well as other patient identifiers and information as applicable by local procedures. The labels will then be affixed to study treatment containers (either sterile syringes or flexible IV bags, as appropriate for the volume of infusate).

A Data and Safety Monitoring Board (DSMB) will be appointed by Baxter Healthcare Corporation to provide ongoing evaluation of safety data (refer to Section 10.8). Reports will be provided to the DSMB at pre-specified intervals.

Blinded data will be entered into the database and the treatment group assignments will be revealed after database lock.

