7.1 Screening Period

After providing written IC, patients will enter the Screening Period. The Screening Period is defined as the period after the ICF is signed and dated until randomization. The maximum duration of this period is 3 days prior to dosing. Randomization is recommended within 24 hours of signing consent but must occur within 3 days of signing consent. If patient is not randomized within 24 hours of informed consent, patient should be started on SOC ILE on Day 1 of PN as per Table 4 and Section 5.3. Signing and dating of the ICF and the Screening visit may occur on the same day, if necessary; however, the ICF must be signed and dated before any Screening activities can be conducted.

The aim of the Screening Period is to determine the eligibility (inclusion/exclusion criteria) of patients for randomization.

Further assessments conducted during Screening include:

- Demographics
- Gestational age and birth weight for infants <1 years of age only
- Medical history (including diagnosis requiring PN)
- Physical examination, including weight and length or height (and head circumference for infants <1 year of age)
- Vital signs
- Laboratory evaluations including hematology and chemistry (refer to Appendix 1, Schedule of Events Table)
- Pregnancy test. Note: All female patients ≥12 years of age must have a negative urine human chorionic gonadotropin (hCG) pregnancy test at screening. For female patients <12 years of age, a urine hCG test at screening will be performed at the discretion of the investigator based on childbearing potential.
- Nutritional intakes
- Medication history
- Randomization to study treatment
- Adverse Events (AEs occurring during Screening but prior to administration of study treatment will be considered as unrelated to study treatment). Non-serious AEs during this time period will be collected as part of the medical history. Serious adverse events will need to be reported as per Section 6.13.7.2.

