10. ADMINISTRATIVE CONSIDERATIONS

10.1 Investigators and Study Administrative Structure

The investigator will comply with the protocol (which has been approved/given favorable opinion by the IRB/), International Council for Harmonisation (ICH) Good Clinical Practice (GCP), the ethical principles of the Declaration of Helsinki, and applicable regulatory requirements as described in the Clinical Study Agreement. The Investigator is ultimately responsible for the conduct of all aspects of the study at the study center and verifies by signature the integrity of all data transmitted to the sponsor. Whenever the term 'investigator' is noted in the protocol text, it may refer to either the principal investigator at the site, or an appropriately qualified, trained and delegated individual of the investigator, except where the investigator's signature is specifically required.

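### The exclusion criteria do not name lipoid nephrosis or acute pancreatitis with hyperlipidemia, both listed in the protocol as Intralipid contraindications

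*Protocol*

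**What the plan says.** Protocol 4.3 has 13 exclusion criteria, and two of them bear on the product labels. Criterion 2 excludes known hypersensitivity to lipid emulsion, egg, soybean protein or any component. Criterion 4 excludes "Patients with severe hyperlipidemia or severe disorders of lipid metabolism characterized by hypertriglyceridemia (triglyceride >400 mg/dL". The synopsis has the same lipid criterion in slightly different form: "characterized by hypertriglyceridemia (i.e. triglyceride >400 mg/dL".

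Section 5.1.1.1 gives two Clinolipid contraindications: hypersensitivity, and "Severe hyperlipidemia (serum triglyceride concentrations above 1000 mg/dL) or severe disorders of lipid metabolism characterized by hypertriglyceridemia". Section 5.1.2.1 says that Intralipid is "contraindicated in patients with disturbances of normal fat metabolism such as pathologic hyperlipemia, lipoid nephrosis or acute pancreatitis if accompanied by hyperlipidemia". That sentence has no severity word and no triglyceride value.

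Enrolment (4.1) follows consent and "confirmation of compliance with the study inclusion/exclusion criteria". Section 7.1 adds: "The aim of the Screening Period is to determine the eligibility (inclusion/exclusion criteria) of patients for randomization". Those kept unaware of the assignment under 5.5 include "Investigator and site personnel; or by the personnel at the central laboratory".

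**The concern.** The exclusions follow the Clinolipid label closely but follow the Intralipid label only in part. In a blinded two-arm trial, a contraindication to one product has to be applied to every candidate before randomisation, because the investigator cannot later apply it to one arm only. If a condition appears in the product description but not in the eligibility list, a checklist built from 4.3 will not ask about it. What is at stake is the safety of an occasional child. No estimate or analysis is affected.

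**Working it through.** There is no planned figure to reproduce. The check sets each stated contraindication against all 13 criteria in 4.3 and the key exclusions in the synopsis.

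| Contraindication in the protocol | What in 4.3 reaches it | Result |
|---|---|---|
| Clinolipid: hypersensitivity (5.1.1.1) | Criterion 2, which is wider | Covered |
| Clinolipid: severe hyperlipidemia above 1000 mg/dL, or a severe hypertriglyceridemic disorder (5.1.1.1) | Criterion 4; since 400 < 1000, anyone above 1000 mg/dL is also above 400 mg/dL | Covered |
| Intralipid: pathologic hyperlipemia (5.1.2.1) | Criterion 4, read as the working definition | No gap shown |
| Intralipid: lipoid nephrosis (5.1.2.1) | Not named; caught only if criterion 4 happens to be met | Gap |
| Intralipid: acute pancreatitis with hyperlipidemia (5.1.2.1) | Not named; caught only if the lipid abnormality is severe or triglycerides exceed 400 mg/dL | Gap for milder hyperlipidemia |

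**Other criteria.** Criterion 1 mentions renal failure requiring dialysis and severe unresponsive metabolic disorders, but only as examples of a critical, unresponsive illness. It does not reach either condition as such. No criterion is a general exclusion for a contraindication to either product.

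**Illustration.** Take a child with acute pancreatitis and an assumed triglyceride level of 300 mg/dL, whose hyperlipidemia is not judged severe. Since 300 < 400, criterion 4 is not met, and no other criterion names the diagnosis. The child passes 4.3, although 5.1.2.1 lists the condition.

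**Route to exposure.**
1. The child is eligible on the listed criteria (4.1, 7.1).
2. Allocation is 1:1 (5.4), and the investigator does not know the arm (5.5). The child may be given Intralipid directly.
3. If allocated to Clinolipid, the child may still reach Intralipid. Section 6.8.3 directs a switch when deficiency persists at maximal lipid intake, and 6.8.4 does so for non-response in a child deficient at baseline. Section 6.14 then takes a rescued patient out of the trial, but the switch itself is a protocol instruction.

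**Ambiguous wording.** In 5.1.2.1 the condition about accompanying hyperlipidemia may qualify pancreatitis alone or the whole list. On the wider reading, lipoid nephrosis counts only with hyperlipidemia. A child with lipoid nephrosis, non-severe hyperlipidemia and triglycerides at or below 400 mg/dL would still pass criterion 4, so the gap narrows but remains.

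**The case against.** The strongest reply is that the rule already exists. Section 5.1.2.1 is part of the protocol, and 10.1 says: "The investigator will comply with the protocol". An investigator who knows that either product is possible can see before enrolment that the contraindication applies. The investigator may end participation at any time in the patient's interest (6.14), and the pharmacist knows which product is being prepared (5.5). All of this stands and keeps the point small. None of it is an eligibility check, however: withdrawal acts after exposure, and the protocol gives the pharmacist no task of screening diagnoses.

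A second reply is that such children will be rare. The example diagnoses in 6.3 are prematurity, gastrointestinal disease and sepsis. That list is illustrative, but the reply is fair.

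A reader might also infer that 4.3 leaves every Intralipid contraindication at least partly open, including hyperlipemia at or below 400 mg/dL. The documents do not support this. In criterion 4 the number follows the limb on lipid disorders, so severe hyperlipidemia can be read as carrying no cut-off. Section 5.1.2.1 sets no threshold for pathologic hyperlipemia, and 6.8.3 itself calls triglycerides above 400 mg/dL severe. Nothing shows that a child at or below that level has the pathologic form.

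A reader might likewise turn the 1:1 allocation into a figure for risk added by the trial. The documents give no frequency for these conditions. Intralipid is described as standard of care (1, 5.1.2), and standard-of-care lipid may start before Screening (5.3), so the excess over usual practice cannot be derived.

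**Conclusion.** The point holds, and it is minor. Two conditions that the protocol lists as Intralipid contraindications are missing from the criteria that decide eligibility: lipoid nephrosis, and acute pancreatitis with hyperlipidemia that is not severe and does not exceed 400 mg/dL. The Clinolipid contraindications are covered.

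The conclusion rests on two readings: that sites judge eligibility from 4.3, as 4.1 and 7.1 indicate, and that criterion 4 serves as the definition of hyperlipemia. I assume few such candidates. If there were none, the omission would have no practical effect. The gain from closing it is a small improvement in safety. The contraindication is not absent from the protocol; it is stated in 5.1.2.1 but not tied to the eligibility check.

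**What to change.** Add one exclusion to 4.3 and to the synopsis: *Patients with lipoid nephrosis, or with acute pancreatitis accompanied by hyperlipidemia.* Leave criterion 4 as it is, as the operational definition of hyperlipemia.

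Naming the two conditions is better than excluding any contraindication to either product. The wording in 5.1.2.1 is open-ended and has no threshold, so importing it whole would leave sites to decide which moderate triglyceride values disqualify a child.

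The cost is one line, carried in an amendment with the IRB review that 10.2 requires, and a few candidates who become ineligible. Medical history, including the diagnosis requiring parenteral nutrition (6.3), and triglycerides (Appendix 1) are already collected at Screening, so no new test is needed. No endpoint, analysis or sample-size statement changes.
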